	
has not been previously done on the study subject and a copy of results is not available for verification.
 
 b. Ability to ambulate 8 meters without assistance (canes and other devices allowed); c. Determined by the investigator to be medically stable at Baseline/randomization as assessed by medical history, physical examination, laboratory test results, and electrocardiogram testing. Subjects must be physically able and expected to complete the trial as designed; d. Minimum of 6 years of education; e. Subjects must have adequate hearing, vision, and language skills to perform interviews as specified in the protocol; f. Subjects must be able to understand and agree to comply with the prescribed dosage regimens and procedures; report for regularly scheduled office visits; and reliably communicate with study personnel about adverse events and concomitant medications; g. Women of childbearing potential (WOCBP) and men must be using an acceptable method of contraception to avoid pregnancy throughout the study and for up to 30 day after the last dose of investigational product in such a manner that risk of pregnancy is minimized. The requisite drug interaction studies to determine the interaction of BHV-4157 with oral contraceptives have not been performed to date. It is therefore not possible to determine the efficacy of oral contraceptives as an effective method of contraception for WOCBP who participation this study. Oral estrogen and progestin hormonal contraceptives as a sole method of contraception are therefore prohibited. It is required that all WOCBP use two methods of contraception for the duration of the study (i.e. beginning at first treatment to 30 days after the last dose of study drug). The two methods should include one barrier method (ex. condom with spermicidal gel, intrauterine devices, cervical cap etc.) and one other method. The other method could include oral contraceptives or another barrier method. h. Women of childbearing potential must have a negative serum pregnancy test at screening and a negative urine pregnancy test within 72 hours prior to first dosing. i. SCA subjects (SCA3/dizziness predominant; SCA1, 2, 3, 6 on Riluzole for more than 8 weeks) will not be limited to Inclusion Criteria of Screening SARA score ≥8 or Score of ≥ 2 on gait subsection of the SARA.

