	
either of the following criteria:
 
 i. In the opinion of the investigator will compromise the ability of the SARA instrument to assess underlying ataxia severity; or, ii. Are associated on the INAS instrument at screening with moderate or severe scores on dystonia (at least 3 of 5 items) or spasticity (at least 2 of 3 items) or rigidity (at least 2 of 3 items) d. SARA total score of > 30 points at screening; e. Subjects may not have started physical or occupational therapy within one month of screening and are not expected to start such therapy during the randomization phase. Subjects with ongoing occupational or physical therapy may be allowed to continue as long as the intensity remains unchanged from two months prior to screening throughout the randomization period. 
2. Medical History Exclusions
 
 a. Clinical history of stroke. Note: Subjects with a history of transient ischemic attack (TIA) may be enrolled, if it occurred at least 3 months prior to screening and the subject is prescribed appropriate treatment [e.g., platelet aggregation inhibitors]; b. Immunocompromised subjects. Note: Subjects taking a systemic immunosuppressive agent may be randomized only if they are on a stable dose, have no clinically relevant immunosuppression, and have a white blood count (WBC) within normal limits; c. Active liver disease or a history of hepatic intolerance to medications that in the investigator's judgment, is medically significant; d. History of medically significant gastrointestinal (GI) illnesses including: 
 i. A current diagnosis of active, peptic ulceration or gastrointestinal bleeding within the last 6 months and/or chronic inflammatory bowel disease at screening; ii. A history of any gastrointestinal surgery that impacts the absorption of study drug; iii. Chronic or frequent episodes of loose stools; bowel movements; e. Vitamin B12 or folate deficiency Note: Subjects with a B12 deficiency can participate in the study if they are on stable Vitamin B12 replacement for at least 3 months prior to randomization and their B12 levels are within normal limits prior to randomization; f. Hematologic or solid malignancy diagnosis within 5 years prior to screening. (Note: Subjects with a history of localized skin cancer, basal cell or squamous cell carcinoma, may be enrolled in the study as long as they are cancer free prior to randomization. Subjects with other localized cancers (without metastatic spread) who have previously completed their course of treatment more than 2 years prior to baseline, are not currently receiving treatment and have been in remission may be enrolled only if, in the opinion of the investigator, there is no expectation for recurrence or further cancer

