--	--

	
allowed;
 
j. Chronic NSAID use (e.g., naproxen, acetylsalicylic acid, ibuprofen) should be treated with proton pump inhibitors unless otherwise clinically prohibited;
 
k. Medical marijuana use within 30 days of baseline visit (and subjects will be expected to refrain from use during the period of the study).

Concomitant Medications:	
 1. Antidepressant Use: The use of tricyclic antidepressants and monoamine-oxidase (MAO) inhibitors are prohibited 30 days prior to screening and during the study. Other antidepressants (e.g., bupropion, citalopram, escitalopram, fluoxetine, mirtazapine, paroxetine, sertraline, venlafaxine, and duloxetine) are permitted if the subject has been treated with a stable dose for 3 months prior to randomization and no dose changes are expected throughout the randomization phase of the study. 2. Hypnotic Use: New use of hypnotics should be avoided. For the management of persistent sleeping difficulties or insomnia, subjects may receive the following medications at the indicated doses (or equivalent doses in countries outside of the US) such as: 
 • zolpidem tartrate (Ambien): up to 10 mg at bedtime (HS) as needed (prn) • zolpidem tartrate extended-release (Ambien CR-): 12.5 mg at HS prn • zaleplon (Sonata): 20 mg at HS prn eszopiclone (Lunesta): 3 mg at HS prn
Screening Procedures:	
 • Eligibility assessments include: Inclusion/exclusion, medical history, demographics, disease history, neurological exam, Mini Mental State Exam, and pregnancy testing for WOCBP at screening and 72 hours prior to first dose. • Safety assessments include: Laboratory assessments, physical exam, physical measurements, vital signs, 12-lead ECG, concomitant medication review, Beck Depression Inventory (BDI), Beck Anxiety Inventory (BAI), and Sheehan Suicidality Tracking Scale Sheehan (STS). • Clinical outcome assessments include: The Scale for the Assessment and Rating of Ataxia (SARA), Inventory of Non-Ataxia Symptoms (INAS), 9 Hole Peg Test, 8 Meter Walk, Clinical Global Impression of Change (CGIC), Patient Global Impression of Change Scale (PGIC); and dizziness assessments (SCA3/dizziness predominant subjects only).
Randomization Phase:	N/A All subjects will receive open drug during the initial 12 weeks of the study.

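### Do the references to a randomization phase in an unrandomized trial, and two differing memantine items, leave rules that cannot be applied?

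*Protocol*

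**What the plan says.** All references are to the Protocol, the only document at hand.

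- **Design.** The Study Design row describes a single-center open study with 12 weeks of dosing, followed by an optional extension of 36 weeks. The Randomization Phase row reads "N/A All subjects will receive open drug during the initial 12 weeks of the study".
- **Physical and occupational therapy (exclusion 1e).** Subjects must not have started such therapy within a month of screening and "are not expected to start such therapy during the randomization phase". Those already in therapy may continue "as long as the intensity remains unchanged from two months prior to screening throughout the randomization period".
- **Antidepressants (Concomitant Medications, item 1).** Permitted agents need a stable dose for 3 months beforehand, and it is required that "no dose changes are expected throughout the randomization phase of the study".
- **Other uses of the word.** Inclusion 3c has "Determined by the investigator to be medically stable at Baseline/randomization"; exclusion 2b has "may be randomized only if they are on a stable dose"; exclusion 2e has "stable Vitamin B12 replacement for at least 3 months prior to randomization" and repeats the word for B12 levels; exclusion 2f has "as long as they are cancer free prior to randomization". The antidepressant item also counts its 3 months back from randomization.
- **Memantine.** Exclusion 4g lists memantine with three other Alzheimer's drugs. It accepts either no use for at least 3 months before Baseline or a stable dose over that time. Exclusion 4h rules out memantine from 30 days before screening and throughout the study.

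**The concern.** A rule tied to a phase that does not exist has, read literally, no start and no end. That matters most for the unchanged-intensity condition in exclusion 1e. This is an uncontrolled trial with SARA at 12 weeks as its primary measure. If therapy intensity changed during treatment, there would be no comparison arm to absorb the effect, and staff need to know when a change counts as a deviation. The text also never says outright whether the condition carries on into the extension.

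The memantine items look like a plain contradiction in eligibility. A candidate on a stable dose for 3 months satisfies 4g and is barred by 4h. The drug-free windows also differ in length and in the date from which they are counted. Two screeners could therefore seem to have grounds for different decisions on the same person.

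**Working it through.** No sample size, power or error rate is involved. The check is a reading of the passages side by side, with a count and one short calculation.

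**Step 1: count the uses of randomization or randomized.**

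| Place | Uses | Kind |
|---|---|---|
| Inclusion 3c | 1 | time point |
| Exclusion 1e | 2 | window |
| Exclusion 2b | 1 | time point |
| Exclusion 2e | 2 | time point |
| Exclusion 2f | 1 | time point |
| Concomitant Medications 1 | 2 | one time point, one window |
| Randomization Phase row | 1 | label |

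Total: 1 + 2 + 1 + 2 + 1 + 2 + 1 = 10. Time points: 1 + 1 + 2 + 1 + 1 = 6. Windows: 2 + 1 = 3. Label: 1.

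**Step 2: the six time points.** Inclusion 3c joins Baseline and randomization with a slash, which gives the word a meaning as a date. All six can be read as Baseline.

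**Step 3: the three windows.** Two of them (no expected start of therapy, no expected antidepressant dose change) are expectations judged at enrolment. Only the unchanged-intensity sentence is a continuing condition. For its length, the protocol offers three pointers:

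- The Randomization Phase row says what takes the place of that phase: the first 12 weeks of open drug.
- The Extension Phase has its own row, and the Subject Safety row separates the initial 12 weeks from an extension running from Week 12 to Week 48 (12 + 36 = 48).
- Exclusions 4b and 4d to 4h use a whole-study term where the whole study is meant. A narrower term in 1e suggests a part of the study, and treatment has only two parts, the second of which is separately named.

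All three point to the initial 12 weeks. Twelve weeks is also the only time attached to any efficacy objective (SARA as primary, INAS as exploratory). On this reading the condition reaches the primary assessment.

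**Step 4: a memantine user on a stable dose.** Exclusion criteria are taken to operate together, so meeting any one of them excludes. The stable user passes 4g and fails 4h, and is excluded. The stable-dose option in 4g then has no effect for 1 of its 4 named drugs; the other 3 are untouched. The outcome is the same for every such candidate.

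**Step 5: a former memantine user.** Let S be the days from screening to Baseline, and take 3 months as 91 days. 4g's drug-free option needs 91 drug-free days at Baseline, and 4h needs 30 + S. Both hold when the drug-free time is at least max(91, 30 + S). The protocol gives no value for S, so three are assumed for illustration:

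| S (assumed) | 4g needs | 4h needs | Both need |
|---|---|---|---|
| 0 | 91 | 30 | 91 |
| 42 | 91 | 72 | 91 |
| 84 | 91 | 114 | 114 |

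Both windows can always be met, and the longer one governs. They overlap; they do not contradict each other. A range for S should not be taken from the 12-week (84-day) laboratory allowance, which limits the age of the tests at Baseline and not the gap between visits. Exclusion 3k lets the tests precede the Screening visit by up to 6 weeks (42 days). With tests that early, at most 84 − 42 = 42 days would remain.

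**The case for a change.** The best case for a change is that eligibility and concomitant-treatment rules belong in the protocol and are not left to a statistical analysis plan, so the absence of that plan excuses nothing. No sentence equates the randomization phase with the initial 12 weeks. Whether the therapy condition continues in the extension is inferred from layout alone. Applying 4g and 4h together yields an answer only by emptying words that 4g expressly applies to memantine, and the drafter's intent stays unknown. The correction would cost a few words and would leave sample size, visits and assessments unchanged.

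Most of this is accurate. The three window phrases do lack a stated equivalent, and the stable-dose option in 4g does disagree with 4h. What does not stand is the step from untidy wording to a defect in the trial. An inferred window is not an absent one when every pointer leads to the same 12 weeks. The silence about the extension concerns a separately named phase that starts after the primary assessment. An unclear intent behind 4g does not produce divergent enrolment if the criteria are applied together. A low cost of correction is a reason to tidy the text, but it does not show a gain in bias, precision, safety or the ability to answer the question.

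**Conclusion.** The concern does not call for a change to the plan. The randomization wording is a clerical slip, apparently text kept from a randomized design. It affects three window phrases, of which one is a continuing condition, and a reader of the surrounding rows would resolve it sensibly. The memantine wording is a genuine but minor inconsistency, confined to one of four drugs in 4g. The passages should be reconciled when the text is next edited, and which memantine rule was intended is for the sponsor to say.

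No stated figure changes, and no effect on the SARA result or on safety is shown. The number of candidates affected is not given; planned enrolment is at most 24. The conclusion rests on two assumptions: that staff read the phase as the initial 12 weeks, as the context indicates, and that exclusion criteria apply together. If the second failed in practice, enrolment of memantine users could vary between screeners, but nothing in the protocol suggests the criteria are alternatives.

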Extension Phase:	Subjects completing the initial 12 week open-label administration will be offered and additional 36 weeks of open-label extension treatment (as allowed by the FDA) as long as the PI believes continued open-label treatment offers an acceptable risk-benefit profile.
Drug Administrations:	Subjects will receive oral BHV-4157 (140 mg QD).

Laboratory Assessments and Sample Collection:
	
 • Laboratory Assessments: All laboratory testing should be done fasting and testing will include the following. Laboratory testing designated as Screening can be done up to 12 weeks prior to the Baseline visit: 
 a) Hematology: hemoglobin, hematocrit, red blood cells, white blood cells, differential count and absolute platelet count [Screening, Week 12, Week 24, Week 36, and Week 48]. b) Serum Chemistry: albumin, sodium, potassium, chloride, calcium, AST, ALT, LDH, alkaline phosphatase, GGT, CPK, total protein, total bilirubin, glucose, creatinine, blood urea nitrogen (BUN), uric acid, triglycerides, total cholesterol, HbA1C, P- Amylase or Lipase, TSH, T4, and urine pregnancy testing will be performed at Screening. Urine pregnancy testing will be repeated at Baseline (up to 72 hours prior) and Week 12. AST, ALT, LDH, alkaline phosphatase, GGT, and total bilirubin will be repeated at Week 12, Week 24, Week 36, and Week 48. c) Urinalysis: macroscopic examination, pH, specific gravity, ketones, nitrites, bilirubin, urobilinogen, leukocyte esterase, protein, glucose, and occult blood will be performed at Screening. d) HBsAg, HCV and HIV antibody detection will be performed at Screening 
Any lab value outside of the normal range must be brought to the attention of a physician (Investigator or Sub-Investigator) at the site. The Investigator will indicate whether or not a flagged value is of clinical significance.
 
 • BDNF Blood Sample Collection: N/A • Pharmacogenetic Blood Sample Collection: N/A • Pharmacokinetic Sample Collection: N/A

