Subject Safety:	
Initial 12 week open-drug administration
 
 • Review of subject eligibility before dosing; • Concomitant medication review: At Screening, Baseline, and through the 2-week Post Last Dose; • Physical examination at Screening, Baseline, and Week 12 • Physical measurements and vital signs will be done assessed at Screening, Baseline, and Week 12; • The Beck Depression Inventory (BDI) and The Beck Anxiety Inventory (BAI) will be assessed at Screening, Baseline, and Week 12. The Sheehan Suicidality Tracking Scale (Sheehan STS) will be assessed at Screening and all visits through the 2-Weeks Post Last Dose Visit; • 12-Lead ECG will be done at Screening and Week 12; • Hematology, serum chemistries, and urinalysis at screening. • CBC and Liver Function Tests will be done at Screening and Week 12; • Urine pregnancy testing will be performed on WOCCBP at screening, baseline, and Week 12. Urine pregnancy testing may also be done at the discretion of the Investigator. • Subjects will be monitored throughout the study for adverse events. 
Extension Phase [Week 12 through Week 48]
 
 • Physical examination will be assessed at Baseline/Week 12, Week 24, Week 48, and 2-Weeks Post Dose; • Physical measurements and vital signs will be assessed at Baseline/Week 12 visit through 2-Weeks Post Last Dose; • The Beck Depression Inventory (BDI) and The Beck Anxiety Inventory (BAI) will be assessed at Baseline, Weeks 24, 48 and 2-Weeks Post Dose. The Sheehan Suicidality Tracking Scale (Sheehan STS) will be assessed at Baseline/Week 12 visit through 2-Weeks Post Last Dose; • 12-Lead ECG will be done at Baseline/Week 12. • Hematology, serum chemistry, and urinalysis at Baseline/Week 12.

	
 • CBC and Liver Function Tests will be done at Baseline/Week 12, Weeks 24, 36, 48 and 2-Weeks Post Last Dose; • Urine pregnancy testing will be performed on WOCBP at Baseline/Week 12 and at the discretion of the Investigator. • Subjects will be monitored throughout the study for adverse events.

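### A subject who stops before Week 12 has no scheduled liver test or CBC after the first dose

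*Protocol*

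**What the plan says.** Under Subject Safety, the list for the initial 12 weeks states: "CBC and Liver Function Tests will be done at Screening and Week 12". The list for the extension is longer: "CBC and Liver Function Tests will be done at Baseline/Week 12, Weeks 24, 36, 48 and 2-Weeks Post Last Dose".

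Laboratory Assessments and Sample Collection gives the same initial schedule. Hematology reads "differential count and absolute platelet count [Screening, Week 12, Week 24, Week 36, and Week 48", and the liver panel ends "GGT, and total bilirubin will be repeated at Week 12, Week 24, Week 36, and Week 48". That section has no draw at Week 4, Week 8, discontinuation or after the last dose. It also says that "Laboratory testing designated as Screening can be done up to 12 weeks prior to the Baseline visit".

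Entry to the extension depends on finishing the first period: "Subjects completing the initial 12 week open-label administration will be offered and additional 36 weeks of open-label extension treatment".

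Study Design has subjects seen every 4 weeks during the initial phase, with a safety follow-up two weeks after stopping and a termination visit for everyone two weeks after the last dose. It does not say what is done at that visit. The initial-phase list under Subject Safety assigns it the concomitant medication review and the Sheehan STS, which "will be assessed at Screening and all visits through the 2-Weeks Post Last Dose Visit". Adverse events are monitored throughout.

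**The concern.** Liver function tests and CBC are named safety assessments under Study Endpoints, and safety and tolerability is a secondary objective. Study Rationale attributes dose-dependent liver test effects to riluzole and offers only a possibility that the prodrug will be safer.

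Subjects who leave before Week 12 may leave because they tolerate the drug poorly. On the written schedule they contribute no post-dose laboratory value, and a symptomless liver elevation at the time of stopping would not be looked for. Values are then missing for a reason that may be related to the outcome. The direction of any effect on the reported rate is unknown. No analysis plan can recover samples that were never drawn, so this belongs in the protocol.

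**Working it through.** The protocol states no figure to reproduce here. The check sets each listed liver test and CBC time point against the visits a subject would attend.

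**Scheduled liver tests and CBC, by type of subject**

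| Subject | Draws listed after first dose | Draw two weeks after last dose |
|---|---|---|
| Stops before Week 12 | none | none listed |
| Completes Week 12, no extension | Week 12 | none listed |
| Enters the extension and completes it | Weeks 12, 24, 36, 48 | listed under Subject Safety, absent from Laboratory Assessments |

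Example: stop at Week 6; follow-up at 6 + 2 = Week 8; scheduled draws since first dose = 0.

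The omission does not look like shorthand. The initial-phase list names the two-week visit for two assessments and leaves blood tests out, while the extension list includes them.

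For a completer, the two initial-phase draws can be up to 12 + 12 = 24 weeks apart, because the screening sample may be 12 weeks old at Baseline. The longest on-drug interval without a scheduled test in this phase is 12 weeks.

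**Effect on the safety summary**

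The maximum enrolment of 24 comes from Subjects. The number of early stoppers, k, is not in the documents; I assume k = 1 to 6.

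- Share without a post-dose value: k/24 = 1/24 = 4.2% to 6/24 = 25.0%.
- Subjects with a value: 24 − k = 23 down to 18.
- If x elevations are observed, the true count among all 24 lies between x and x + k. The proportion is therefore undetermined by k/24, that is 4 to 25 percentage points.
- With zero elevations observed, the one-sided 95% upper limit is 1 − 0.05^(1/n):
  - n = 24: 11.7%
  - n = 23: 12.2%
  - n = 18: 15.3%

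The upper limit thus rises by 0.5 to 3.6 percentage points. It also assumes that the subjects with values represent those without, which is doubtful if stopping is related to tolerability.

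**The case against.** The strongest reply is that this is silence about an unplanned event. For the initial phase the two sections agree. A visit two weeks after the last dose already exists for everyone, and the extension attaches the draw to a visit of the same name, so a site could carry it over. A subject who stops near Week 10 has a follow-up near Week 12 and might be given the Week 12 tests. Investigators can also order unscheduled tests. All of this is possible, but the text requires none of it, and the Week 12 overlap does not help anyone who stops earlier.

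Other safeguards exist. The protocol excludes medically significant active liver disease or hepatic intolerance (Exclusion 2c), raised liver tests at screening (Exclusion 3c) and previous riluzole intolerance (Exclusion 4a). It requires medical stability at Baseline (Inclusion 3c) and monitors adverse events. These reduce the risk, but none schedules a post-dose test in an early stopper.

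Several points do stand:

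- The stopping rate is assumed, and the effect on the upper limit is small in an uncontrolled study of up to 24 subjects.
- The ECG and vital signs have the same gap for early stoppers in the initial phase.
- The concern is weaker for the up to 4 subjects who switch directly from riluzole, since they already have exposure to the active moiety.
- Completers who do not extend already have a Week 12 draw at the end of dosing, so for them a later draw is a matter of consistency with the extension.

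**Conclusion.** The concern holds. As written, a subject who stops before Week 12 has zero scheduled liver tests or CBCs after the first dose, and a completer who declines the extension has none after Week 12. The first conclusion follows from the text and needs no assumption beyond reading the schedule as complete.

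The size of 4 to 25 percentage points rests on 1 to 6 early stoppers among 24. The loss of precision is modest; the greater weight lies on the individual subject's safety and on selective missing values. This should be corrected, but it does not undermine the study as a whole.

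Two smaller inconsistencies are real. Laboratory Assessments omits the post-last-dose draw that Subject Safety lists for the extension. Separately, Inclusion 3h requires a negative serum pregnancy test at screening, while both schedules list only urine testing. A site working from the schedules alone would miss the serum test, although eligibility review and the urine test within 72 hours of dosing limit the harm.

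**What to change.** **Main change.** In Subject Safety and in Laboratory Assessments, require liver tests and CBC:

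1. at discontinuation, or as soon as possible afterwards, for any subject who stops between scheduled draws; and
2. at the visit two weeks after the last dose for every subject, including early stoppers and completers who do not extend.

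Adding both time points to the hematology and liver chemistry entries also brings Laboratory Assessments into line with the extension list. Every early stopper who attends would then have a value at or near the end of dosing and another two weeks later. A general rule to perform the Week 12 safety assessments at early stopping would serve for the first time point and would also cover the ECG and vital signs.

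**Cost.** A protocol amendment and some extra draws. The section says "All laboratory testing should be done fasting and testing will include the following", so each added draw means a fasting visit.

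- All completers extend: at most 2k = 2 to 12 draws for k = 1 to 6.
- No completer extends: at most 2k + (24 − k) = 25 (k = 1) to 30 (k = 6).
- Add one draw for anyone who stops between extension visits.

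The post-dose draw uses an existing visit; the discontinuation draw may need an extra one.

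**Optional, and not the correction of an error.** Add draws at Baseline and at the existing Week 4 and Week 8 visits. This shortens the longest on-drug interval in the initial phase from 12 to 4 weeks, at a cost of at most 3 × 24 = 72 further fasting draws.

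**Separately.** List the serum pregnancy test at Screening in both schedules and keep the urine test at Baseline. Blood is already drawn at Screening, so no visit is added.
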